In parallel, the kinetics of nasopharyngeal and faecal virus shedding (duration) in relation to symptom onset and severity are both unknown for the novel A/H1N1 virus, but highly relevant in relation to estimation of the likely period of infectivity and in relation to virus replication and therapeutic management (in particular, optimal duration of antiviral drug therapy). In all previous research on influenza virus excretion, shedding has been determined by measurement of the quantity of virus recoverable from the patient's nasopharynx by the deliberate insertion of a cotton swab, nasopharyngeal aspiration or the performance of a nasal wash; i.e. virus has been recovered by a deliberately performed invasive technique. Whilst this data is useful, we propose that these data should be linked to near-patient environmental sampling which would determine the extent to which infectious virus has been deposited onto surfaces and into the air in the patient's inamediate vicinity (thus allowing an estimation of the potential for contact transmission) and the measurement of infectious virus in air according to particle size and distance from the patient. We believe that the correlation of virus shedding data against environmental contamination via linked data is critical translational research that will assist policy development far more effectively than virus shedding data obtained in isolation.

Our consortium already has experience in performing virus shedding studies in experimentally infected patients with influenza and virus sampling and virus survival work in relation to contaminated surfaces. It also has air sampling equipment provided on loan from the US Centers for Disease Control (CDC) and the National Institute for Occupational Safety and Health (NIOSH) which has been validated for use with patients with confirmed influenza infection. Although the findings of this research will clearly have long-term relevance to influenza infection control practices, given the strong likelihood of significant pandemic activity by mid-late autumn 2009, the emphasis will be on gaining early data from pandemic influenza patients in August and September 2009, with the intention of providing an early 'policy steer' as well as a longer-term answer.

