- iii) To describe virus shedding (quantity of infectious virus) and duration according to important patient sub-groups, notably adults and children, those with mild illness (community patients) and those with more severe disease (hospitalised patients)
- To determine if aerosol generating procedures (most likely to be performed on ITU) are associated with changes in the quantity of environmental contamination with live virus, either in relation to quantity or particle size, or distance from source.
- v) To investigate the possibility of estimating the number of influenza-infected individuals in an area by the quantity o influenza virus recovered in sewage influent.

Policy related (to provide scientific data suitable for policy refinement on):

- vi) 'Safety distances' around patients with pandemic and seasonal influenza
- vii) Appropriate use of respiratory personal protective equipment (RPPE) and infection control practices for pandemic and seasonal influenza, according to patient type, illness severity and time since symptom onset
- viii) Antiviral treatment duration for patients with pandemic influenza
- ix) To develop an alternative surveillance strategy for quantifying influenza infections in a community.

The primary objective of this study is to correlate the amount of virus detected in a patient's nose with that found in the environment around them and with the time since illness onset and symptom severity. The point being that so called 'virus shedding' studies that measure virus recovered from the nose do not actually define environmental contamination and hazard to others. To the best of our knowledge such work has not been done before. The study has the potential to address the issues of how, when and where in relation to virus transmission, all of which we believe could inform policy. By collecting stools, we can also correlate influenza shedding in the nose with the stool and thereby provide a mechanism for generating estimates of influenza in the stool to populate the sewage-based epidemiology model.

How – Are touched surfaces important in virus transmission and does respired air present a significant transmission route?

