- 4. In order to ensure that patients with relatively recent onset of symptoms are recruited we will set exclusion criteria of >48h after symptom onset for community cases (but aim for recruitment of cases who are within 24h of symptom onset); and > 96h after symptom onset for hospitalised cases (but aim for recruitment within 48h).

Study Management

The study will be managed from a central coordinating site (Nottingham University) by a project manager and administrator. Data will be collected on to source documents and CRFs by the clinical team. Data will subsequently be entered onto a database. All data will be stored at the

University of Nottingham and they will act as custodian of it. Data generated from CEH will be shared with the project team and stored along with the rest of the virus shedding data.

Duration of the study and participant involvement

Each participant's involvement with the study will last for up to 2 weeks. No further follow up of participants is planned. Enrolment will begin in August 2009 and will cease in October 2009. Processing of samples collected and data extraction will continue until February 2010

End of the Study

The end of the trial will follow the completion of the laboratory analysis of samples and subsequent data analysis and presentation.

9. Selection and withdrawal of participants

See Appendix 1 for study outline

Cases

We propose the study of small numbers of symptomatic pandemic influenza patients from four groups:

- i) Hospitalised adults
- ii) Hospitalised children (up to the age of 16 years)
- iii) Adults in their own homes
- iv) Children in their own homes (up to the age of 16 years)

We regard these four groups as the minimum desirable based on known differences in virus shedding and respiratory etiquette between adults and children and likely differences in symptom severity between patients managed in the community and those who require hospital admission.

Hospital cases once discharged will be followed up and further sampling will take place in the patient's own home with consent. Similarly if a community patient is admitted to hospital mid-way through sampling we would attempt to follow them up in hospital.

Recruitment

HOSPITAL CASES:

Hospital cases will be identified through the clinical teams looking after patients in the participating centres.. We will not receive personal information about patients or approach them until their consent for us to do so has been granted.

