We will advertise in the local press for volunteers with flu like symptoms to take part in the study. The advert will invite people who have or who develop a flu-like illness to participate in a research study that aims to improve our understanding of how swine flu is transmitted between people. We will ask people who are interested in helping to call our research office. Preliminary details will be obtained to establish their potential eligibility and an appointment will then be made for a member of the research team to visit the patient at home. Advertising in this way should enable us to pick up patients early in their illness. Adverts will run once a week for 4 weeks depending on recruitments rates.

2. Antiviral Collection Points

A back up to our planned recruitment via the local media will be to recruit patients who have been diagnosed with swine flu and who have been issued with a 'prescription' for oseltamivir. When a patient's family member or 'flu friend' collects the medicine from a designated collection point, a leaflet will be given out that describes our study and invites people to take part. Interested patients will be asked to ring our research office for further information and we can then establish their eligibility.

This method of recruitment gives us access to a significant number of people already clinically confirmed to have swine flu. A drawback is that we would only be able to recruit patients taking

oseltamivir, i.e. we would not be study the natural course of infection in this group. Furthermore, by using this approach it may be that some cases have had symptoms for some time before we make contact with them.

We have the support of the director of Public Health for Nottingham PCT ([name]) for this recruitment mechanism.

3. University of Nottingham

We will make contact with both well and unwell (symptoms of acute respiratory infection) students at the University of Nottingham through the student health centre and university accommodation / halls of residence.

- Unwell students would be asked to take part and then assessed for study eligibility
- Contacts of unwell students would be sought and asked to take part if they become unwell
- Well students would be asked to contact us should they become unwell

Case definitions:

There are a number of options available to us in defining the patients we wish to recruit;

- 1. Formal virological diagnosis of novel influenza A or novel A(H1N1) swine flu

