- Near-patient test positive for influenza A or other substantive test positive for influenza A (including 'swine flu')
- Willing to participate and agrees to allow both nasal and environmental samples to be taken

Exclusion criteria:

- Illness for >48h (community cases)
- Illness for >96h (hospital cases)
- A negative for swine flu (as part of NHS care)
- Has taken part in influenza research involving an investigational medicinal product within the last 3 months

Randomization

Randomisation to the days of surface swabbing will occur. 50% of participants will have surface swabbing done on alternate days from the first visit whilst the other 50% will have swabbing done on alternate days from the second visit. Envelopes will contain instructions to 'swab from Day 1' or 'swab from Day 2' in a 1:1 ratio. The envelopes will be identical and number of them will be given to each study nurse who will open an envelope following enrolment of a participant.

Participant Withdrawal

Participation in this study may be discontinued for any of the following reasons:

- 1. The wish of the subject. A subject can withdraw from the study at any time, for any reason, without prejudice to their future medical care. Participants will be made aware (via the information sheet and consent form) that should they withdraw the data collected to date cannot be erased and may still be used in the final analysis.
- 2. Non compliance with study procedures.
- 3. If a patient has a virological test that is negative for swine flu as part of NHS care.
- 4. Investigator's decision that withdrawal from further participation would be in the subject's best interest.
- 5. Termination of the study by the Investigator or Sponsor.

Data will be collected on participants who are withdrawn with outlining the reason(s) for discontinuation.

Criteria for terminating the study

Termination of the study as a whole may result from new information regarding H1N1 or issues with study conduct (e.g. poor recruitment, loss of resources).

Informed consent

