- Daily symptom diary cards This will allow a correlation of illness and viral shedding to be made. It will be completed by the patient on each researcher visit. A sample is attached as appendix 3; this scale has been previously validated in numerous live challenge studies.
- Daily temperature readings. Patients at home will be supplied with a digital thermometer and asked to take twice daily readings and additional readings whenever feeling feverish.
- A record of all medication taken during the follow up period will be kept. This would include paracetamol, aspirin, antivirals and antibiotics.
- Whilst in hospital a log documenting the performance of any aerosol generating procedures will be kept (e.g. aspiration of respiratory tract, intubation, resuscitation, bronchoscopy)
- A log will also be kept of the use of nebulisers as it is possible that the use of these generates aerosols [17].
- Room temperature and humidity records will be kept by the visiting researcher. Recordings will be taken at the beginning of any sample collection.

Sample Collection

We will be collecting the following samples;

- 1. Upper respiratory tract specimens from patients.
- 2. Surface swabs to detect virus on commonly touched surfaces near the patient.
- 3. Air particles to detect virus in room air around a patient.
- 4. Stool samples from patients.

1. Upper respiratory tract specimens;

Consideration has been given to what specimens should be collected for influenza tests from persons with suspected influenza. A number of papers compare the utility of nasal swabs (NS) versus nasopharyngeal aspirates (NPA) in the diagnosis of respiratory viral infections, mostly in children. Whilst the sensitivity of viral detection is slightly higher with NPA (with both PCR and culture diagnostic techniques) NS are regarded as adequate by many, especially for collection done at home where less equipment is needed [18,19,20,21,22]. In addition NS will be easier to manage in terms of staff training and consistency of specimen collection. It is for these reasons that NS will be preferred method of specimen collection. However, we recognise that children may also have NPAs done for therapeutic reasons as part of their normal medical care. In this instance we would still perform a nasal swab.

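### The medication record starts at enrolment, so antiviral doses taken before Day 1, and the date of the first dose, are not required although patients already on treatment are expected

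*Protocol*

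**What the plan says.** The rule is in Section 10, Collection of data: "A record of all medication taken during the follow up period will be kept". Antivirals are among the drugs named there. The sample schedule in Appendix 2 ticks concomitant medication on Days 1 to 12, and Day 1 is also the day of consent. The only other baseline source described is a set of first-visit forms on medical history and current symptoms (Synopsis, Description of interventions). What those forms ask about medication is not given.

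Four other parts of the protocol bear on this:

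- Section 9, Antiviral Collection Points, sets out a back-up recruitment route for people already issued oseltamivir. It concedes that by this route "we would only be able to recruit patients taking" that drug, and that some of them may have been symptomatic for a while.
- The exclusion criteria in Section 9 set the latest entry at 48 h of illness for community cases. For hospital cases the criterion reads "Illness for >96h (hospital cases").
- Section 5 (Virus Shedding) and Section 6 (the part headed When) list antivirals among the factors that affect shedding.
- Section 11 plans a survival analysis of what predicts shedding duration and a test of mean duration in mild against severe cases. It lists medication logs as an outcome measure.

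**The concern.** Shedding is to be described by time since symptom onset, but the antiviral record runs from enrolment. For anyone treated before the first visit, the two clocks are not tied together. The record shows that the patient is on an antiviral on Day 1. It need not show whether that is the first day of treatment or a later one.

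At stake is the use of antivirals as an explanatory variable. Early and late starters would be mixed, and any association between treatment timing and shedding duration could be distorted. The protocol equates mild with community and severe with hospitalised patients, and these two groups have different entry limits. The room for misclassification therefore differs between groups that Section 11 intends to compare.

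This is a rule about what is collected. An analysis plan cannot recover a date that nobody was told to ask for, and Section 8 plans no follow-up after participation ends.

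**Working it through.** The protocol gives no figure on this point. Its power statement for shedding duration (5 against 6 days) compares adults with children, does not involve antivirals, and is not disputed here.

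**Step 1: inputs.**
- Latest permitted entry (Section 9, Exclusion criteria): 48 h community, 96 h hospital.
- Recruitment aims (Section 8, study design principles): 24 h community, 48 h hospital.
- Start of the medication record: enrolment, Day 1 (Section 10; Appendix 2).
- Shedding durations cited for seasonal influenza (Section 10, Upper respiratory tract specimens): 5 days in adults, up to 10 days in young children.

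**Step 2: formula.** Unrecorded treatment interval = time of enrolment − time of first dose. If no dose is taken before onset, this cannot exceed the time from onset to enrolment.

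**Step 3: ceilings.**

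| | Community | Hospital |
|---|---|---|
| Entry at the limit | 48/24 = 2 days | 96/24 = 4 days |
| Entry at the recruitment aim | 24/24 = 1 day | 48/24 = 2 days |
| Limit ÷ 5 days (adults) | 2/5 = 40% | 4/5 = 80% |
| Limit ÷ 10 days (young children) | 2/10 = 20% | 4/10 = 40% |
| Aim ÷ 5 days (adults) | 1/5 = 20% | 2/5 = 40% |

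The hospital ceiling is twice the community ceiling whether the limits (4/2) or the aims (2/1) are used. All of these are upper bounds: they need the first dose at onset and, in the rows for the limit, entry at the last permitted hour.

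**Step 4: how two different patients come to look alike.** Take two hypothetical hospital patients, both enrolled 96 h after onset. A took a first dose at 24 h; B takes a first dose at enrolment.

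- True time from onset to first dose: A 24 h, B 96 h.
- Antiviral use within the recorded window: both from Day 1, that is 96 h.
- Treatment missing from A's record: 96 − 24 = 72 h, or 3 days.

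On the required record, A and B have the same treatment start.

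**Step 5: can the number affected be found?** No. The protocol does not say how many patients will come through collection points, how many of those will have taken doses before the first visit, or how many hospital patients will be treated before enrolment.

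**The case against.** Several counter-arguments have force.

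**A start date may be captured anyway.** The first-visit forms and the Day 1 medication entry are natural places to ask for one, and the forms are not shown. The network through which hospital cases are found also gathers treatment information on admitted patients, though the protocol does not say that these data will be linked. This stands. A reader might infer that first-dose time and total days treated cannot be derived. The text supports only that the protocol does not require them and that its stated window leaves out earlier doses.

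**Treatment status at each swab is known.** Medication is checked daily beside the daily nasal swab, so from Day 1 on-drug or off-drug status, and a last dose during follow-up, are recorded. This stands too. It would be wrong to conclude that the study cannot tell shedding on treatment from shedding after it, apart from patients who stopped before enrolment. What is missing is the start.

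**No group varies treatment duration.** A reader might see a contradiction between the aim "Antiviral treatment duration for patients with pandemic influenza" and a design whose four groups are set by age and setting, and in which only the days of surface swabbing are allocated at random ("Randomisation to the days of surface swabbing will occur"). The documents do not support that reading. The aim sits under "Policy related (to provide scientific data suitable for policy refinement on"), and Section 5 gives its route: shedding kinetics bear on "therapeutic management (in particular, optimal duration of antiviral drug therapy"). It is informed indirectly, promises no comparison of durations, and need not be restated.

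**The percentages are ceilings.** The 40% and 80% figures also rest on the adult 5-day value, and collection points are only a back-up route. This stands. They should not be read as expected error.

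**Conclusion.** The point holds as a defect in a stated data-collection rule. The protocol expects some patients to be on an antiviral at entry, regards antivirals as affecting shedding, and means to model shedding duration, but it limits the medication record to the period after enrolment. Followed literally, it leaves earlier doses unrecorded and can misclassify when treatment began.

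The gap is at most 2 days in the community and 4 days in hospital, falling to 1 and 2 days if recruitment meets its aims. This assumes no antiviral before symptom onset. The share of patients affected, and the resulting bias, cannot be calculated from the document. That antivirals will enter the survival model is an inference from the medication logs and the Background, because Section 11 does not list the predictors.

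The finding does not show that the aim on treatment duration is unattainable, and it does not touch the sample size.

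**What to change.** Amend Section 10, Collection of data, and the Day 1 form so that antiviral use is recorded from symptom onset to the end of follow-up, with date and time of first and last dose. Where antivirals are examined as a predictor of shedding duration, use time from onset to first dose, not presence on the Day 1 record. If the first-visit forms already ask for this, a sentence in Section 10 saying so is enough.

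The cost is one line on a form and a small change of wording. The drawback is some recall error for doses taken before enrolment. No visit, sample, group size or objective changes, and no change to anyone's treatment is proposed.

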Older data suggest that virus shedding is proportional to symptom severity and that virus shedding in adults declines markedly on the third day after symptom onset. Contemporary data on virus shedding in healthy adults derives from studies performed for the licensure of antiviral drugs [3, 4]. It is normally quoted that the shedding of infectious virus (as opposed to PCR detectable virus) is 5 days in adults and CDC infection control guidance reflects this. PCR can detect virus after this time but culture is usually negative. A recent study found that adult patients could shed virus (detected by polymerase chain reaction (PCR) and culture) beyond this traditional period, though patients were elderly and nearly all had underlying medical conditions [5]. Indeed, it is well documented that older patients, those with chronic illnesses and those with immunocompromise can shed live virus for longer periods because virus replication is less inhibited [6]. In the current pandemic however, this may not apply to the elderly because there is already (unpublished) evidence that the level of cross-protective immunity in elderly subjects to the novel A/H1N1 virus is higher than in younger adults and children.

It should be remembered that approximately 50% of all influenza infections are asymptomatic [7] and that infected people (typically adults) can shed influenza virus without any evidence of respiratory symptoms [8]. However, the importance of transmission from infected people during the incubation period or from those with asymptomatic infection is uncertain and is probably substantially less than from symptomatic people.

Children:

CDC guidelines state that children shed virus for up to 10 days

(http://www.cdc.gov/flu/professionals/infectioncontrol/healthcarefacilities.htm). Studies of naturally occurring influenza B infection in children have shown that 93% shed detectable virus during the first three days of symptomatic illness, 74% on day four and roughly 25% on day six and that viral shedding is proportional to severity of illness and temperature elevation [9]. In general, children cease shedding influenza virus seven to eight days after onset of symptoms, but they can shed infectious virus several days before onset of illness [10,11]

Other virus shedding work:

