Despite the above, the detection of *viable* virus in aerosols generated by humans has not been shown before (as far as we know). The generation of information about the presence of viable influenza virus in the environment will be fundamental to our understanding of the routes of transmission. With this in mind, we have recently attempted to demonstrate that viable influenza virus can be found in aerosols as part of the Proof of Concept study (ITSDG-01) mentioned earlier. In preparation for this, the University of Nottingham received sampling equipment from CDC/NIOSH (identical to that used by [name] et al above). Prior to its use we approached the Health and Safety Laboratory in England to pilot setting-up of the sampling equipment, calibration and evaluating the utility of the sampler for capturing live influenza. Following experiments that involved aerosolizing influenza virus in a laboratory, live virus could be detected by an air sampler using the virus plaque assay technique (and PCR results were concordant). Following on from this, air sampling recently took place during the proof of concept study – results are awaited. Thus the technique of air sampling using the CDC/NIOSH equipment has been validated in the UK at the Health and Safety Laboratory and (pending results) during a quarantine based challenge study.

Research at CEH has already demonstrated in preliminary research the capacity of the influenza virus to persist in sewage influent for over 2 hours with only a 60% loss in total counts (quantitative PCR). Given that our ability to detect the virus spans >8 orders of magnitude using quantitative PCR, a 60% decline is negligible (e.g., lowering virus counts from 5.0 x 10^6 to 2.0 x 10^6). Hence, there is every reason to expect that if the virus is being shed by influenza-infected patients, the virus should be recoverable in the sewage influent.

6. Research Objectives

The objectives of the proposed study are:

Primary:

- To determine the quantity of infectious virus present in the nose, on surfaces, in air and in stools, according to time from symptom onset, symptom constellation (e.g. presence of cough or sneeze), distance from source and particle size (in air);
- ii) To correlate serial virus shedding in pandemic influenza patients against data on near-patient environmental contamination (surfaces and air).

Secondary:

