It will be necessary to clean down surfaces following swabbing each day to remove viral genomic material, so that the following days swabs reflect the deposition of new material. This will preferably be done with a chlorine based agent but will depend on the surface. It may then be necessary to was the wash the cleaned surface with distilled water to remove any residue of cleaning agent that may affect virus that is subsequently shed upon it.

Samples will be taken every other day during the period of follow up, i.e. nasal swab one day, nasal swab + surface swabs on the next day. We will randomly allocate patients to have surface swabbing done on either days 1, 3, 5, 7, 9 and 11 or 2, 4, 6, 8, 10 and 12.

Samples will be taken by swabbing 2 cm² areas on selected surfaces from within the rooms housing patients. For consistency we have chosen the following surfaces though we will allow some discretion to be exercised by the researcher;

Hospital;

- Patient table (mid-point or nearest to midpoint)
- Patient line console (e.g. on/off button) / Nurse call button depending on circumstances
- Door handle
- Patient drinking receptacle (cup / glass)

Home;

Virus Shedding Study Protocol Version 1.2, 27AUG2010

Page 24 of 38

- Kitchen Fridge door handle+ kettle handle
- Lounge TV remote control (mid point on the back of the device), light switch
- Bathroom Tap + door handle
- Mobile phone

We expect to obtain 1875 samples in total:

- Hospitalised adults: 12.5 patients (we estimate that 50% of hospital patients will be in side rooms), 12 samples (3 samples every other day for 8 days) = 150
- Hospitalised children: 12.5 patients (we estimate that 50% of hospital patients will be in side rooms), 18 samples (3 samples every other day for 12 days) = 225
- Adults in their own homes: 25 patients, 24 samples (6 samples every other day for 8 days) = 600
- Children in their own homes: 25 patients, 36 samples (6 samples every other day for 12 days) = 900

Method of sampling:

Cotton / fibre tipped swabs to be dipped in tube containing 1.5 ml viral transport medium and then rubbed across 2 cm² area of surface in 6 different directions, applying even pressure. Swab to be broken off into tube containing SFM.

3. Air Particle Collection

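### Surfaces are cleaned only after a swab, so each patient's first surface swab measures standing contamination over an unknown period, while later swabs measure about 48 hours of new deposition

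*Protocol*

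**What the plan says.** Section 10 of the protocol (Surface Swabbing) sets the cleaning rule: "It will be necessary to clean down surfaces following swabbing each day to remove viral genomic material", with the purpose "so that the following days swabs reflect the deposition of new material". The same section fixes the interval: "Samples will be taken every other day during the period of follow up".

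Section 9 (Randomization) staggers the start. Half the patients are swabbed from the first visit, and "the other 50% will have swabbing done on alternate days from the second visit". The instruction is given by envelope: "Envelopes will contain instructions to 'swab from Day 1' or 'swab from Day 2' in a 1:1 ratio".

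Neither section, nor the sample schedule in Appendix 2, contains a clean at enrolment or before the first swab. Because cleaning follows swabbing, the Day 2 arm has no specified clean at its Day 1 visit.

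The surface results serve both primary objectives in Section 6. The first is the quantity of infectious virus on surfaces by time from symptom onset. The second is "To correlate serial virus shedding in pandemic influenza patients against data on near-patient environmental contamination (surfaces and air". Section 11 plans plots of surface quantity against time since onset, tests of correlation, and a generalized linear model with random effects for surface virus. It does not distinguish the first swab from later ones.

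**The concern.** The reason the protocol gives for cleaning is not met for any patient's first swab. That swab measures everything left on the surface up to that moment. Its period depends on how long the patient has been ill, how long they have been in that room, what was shed before symptoms, who else touched the surface and when it was last cleaned in the ordinary way. Later swabs measure what was deposited in the roughly 48 hours since the study's own clean.

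The two quantities then share one time axis and one nose-to-surface correlation. Within a patient the odd one out is always the earliest sampled point, often when nasal titre is high: Section 5 notes that adult shedding falls markedly on the third day after onset. A difference between the first and second surface results may therefore reflect the change in what is measured and not the course of shedding.

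**Working it through.** **1. Reproducing the planned total.** Section 10 gives patients, swabs per sampling day and sampling days for each group.

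| Group | Patients × swabs × days | All swabs | First-round swabs |
|---|---|---|---|
| Hospital adults | 12.5 × 3 × 4 | 150 | 37.5 |
| Hospital children | 12.5 × 3 × 6 | 225 | 37.5 |
| Home adults | 25 × 6 × 4 | 600 | 150 |
| Home children | 25 × 6 × 6 | 900 | 150 |
| Total | | 1,875 | 375 |

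The protocol's 1,875 is reproduced. First-round swabs are 375/1,875 = 20%: 1 in 4 rounds for adults (four sampling days) and 1 in 6 for children (six). This assumes the same surfaces are used at every round; Section 10 allows the researcher some discretion, and a substituted surface would also lack an earlier clean.

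**2. Time covered by the first swab.** Section 9 admits community patients up to 48 h after onset and hospital patients up to 96 h. A Day 2 start adds 24 h. The time T from onset to first swab is therefore:
- community: 0–48 h (Day 1 start) or 24–72 h (Day 2 start);
- hospital: 0–96 h or 24–120 h.

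The hospital values are ceilings, because they count all time since onset as spent in that room.

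**3. Size relative to a later swab.** Assume constant deposition.
- Without loss (an approximation for PCR genome): ratio = T/48.
- With exponential loss at half-life h (infectious virus): ratio = (1 − 2^(−T/h)) / (1 − 2^(−48/h)).

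The protocol gives no half-life. Section 5 (Fomites) cites culture up to 24–48 h on steel and plastic and 8–12 h on cloth, paper and tissues. I assume h = 6 to 24 h.

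| T | Who can have it | No loss | h = 6 h | h = 12 h | h = 24 h |
|---|---|---|---|---|---|
| 0 h | Day 1 start, entry at onset | 0 | 0 | 0 | 0 |
| 24 h | Day 1 start, ill 24 h; or Day 2 start, entry at onset | 0.50 | 0.94 | 0.80 | 0.67 |
| 48 h | Community, Day 1 start, latest entry | 1.00 | 1.00 | 1.00 | 1.00 |
| 72 h | Community, Day 2 start, latest entry | 1.50 | 1.00 | 1.05 | 1.17 |
| 96 h | Hospital, Day 1 start, latest entry | 2.00 | 1.00 | 1.06 | 1.25 |
| 120 h | Hospital, Day 2 start, latest entry | 2.50 | 1.00 | 1.07 | 1.29 |

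These ratios leave out shedding before onset, other people's contamination and ordinary cleaning, none of which the protocol fixes.

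**4. Would dividing by hours since cleaning repair it?** With the same half-lives, a 24 h swab holds 0.67–0.94 of a 48 h swab. Dividing by hours doubles its relative weight (48/24 = 2), giving 1.33–1.88. That overcorrects by more than the upward error being repaired (at most about 1.3 for infectious virus).

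**The case against.** A colleague could answer that there is no contradiction. The cleaning sentence promises new deposition only for swabs taken after a clean, and the first objective asks what virus is present, which an undisturbed surface at entry does show. That stands: the first swab is a valid measurement. The difficulty is that it is a different measurement from the later ones and is not kept apart from them.

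The analysis plan, which is not shown, might flag first rounds. It might, but cleaning is a field procedure, and no analysis can give the Day 2 arm a known accumulation period afterwards.

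A reader might infer that the problem sits on the earliest day of illness and is fully confounded with time since onset. The documents do not support this. First swabs can fall anywhere from about 0 to 120 h after onset, and the random start staggers them further, so they overlap other patients' later swabs. The first swab is the earliest sampled day, and swab round and time since onset are partly separable.

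A reader might also infer large, mainly upward errors. Section 5 says of children that "they can shed infectious virus several days before onset of illness"; adding two to three such days to 48 h of illness and a Day 2 start gives 120–144 h, or 2.5–3 times a later swab without loss. But the protocol gives no pre-symptomatic deposition rate, and calls transmission in the incubation period uncertain and probably substantially less. For infectious virus under the assumed half-lives, even 144 h gives only 1.00–1.31. A hospital window as short as 6 h likewise has no source in the protocol.

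Finally, Section 5 treats a 60% loss as negligible given the PCR assay's range, though for sewage. Upward errors up to 2.5-fold are modest on that scale; the downward end is not limited in the same way.

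**Conclusion.** The point holds in a limited form. One planned surface swab in five measures standing contamination over an uncontrolled period, the rest measure about 48 h of new deposition, and the protocol does not set the two apart. The count rests on the protocol's own numbers. The size of the error rests on assumptions: constant deposition, time since onset only, and either no loss or a half-life of 6–24 h. On those terms the first swab can be well below a later one when entry is early. At the upper end it reaches 1.0–1.5 times in the community and 2.0–2.5 times in hospital without loss, but only about 1.0–1.3 times for infectious virus. The direction is not fixed, and the size does not suggest that the primary objectives are lost. It is a cheap improvement.

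**What to change.** - At the Day 1 visit, wipe the selected areas in the Day 2 arm as well, without swabbing. Its first swab then has a known window of about 24 h.
- Record the clock time of each clean and each swab.
- Keep the first swabs of the Day 1 arm as a measure of standing contamination, marked by a first-round indicator.
- Include that indicator and time since last clean as covariates in the planned random-effects model, and add a sensitivity analysis without first-round swabs.
- Do not express results per hour since cleaning, since that assumes linear accumulation. Do not drop Day 1 swabs from the main correlation, since that discards early pairs when nasal titres are likely to be high.

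The cost is a few minutes of wiping at a visit that already takes place and one extra time field. The Day 2 arm's first window is 24 h and not 48 h, which the time covariate must carry. With 1:1 allocation, about 188 swabs (375/2, or 10% of 1,875) remain standing-contamination measurements. Patients already sampled cannot be given a baseline clean, but their first-round swabs can still be flagged.
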